## 8.7 Study Termination

The study may be stopped at any time by the Investigator and/or [REDACTED] after consultation with the Sponsor, with appropriate notification.

## 8.8 Study Duration

An individual subject's participation will involve 7 visits over approximately 48-weeks (336 days)

## 8.9 Monitoring and Quality Assurance

During the course of the study a monitor, or designee, will make routine site visits to review protocol compliance, assess study drug accountability, subject safety, and ensure the study is being conducted according to the pertinent regulatory requirements. The review of the subjects' medical records will be performed in a manner that adequately maintains subject confidentiality. A monitoring plan will outline further details of the study monitoring.

OC-01 (varenicline) Nasal Spray  
Clinical Trial Protocol # OPP-101  
Amendment #1

Sponsor: Oyster Point Pharma, Inc.

Regulatory authorities of domestic and foreign agencies, Sponsor quality assurance, [REDACTED], quality assurance and or its designees may carry out on-site inspections and/or audits, which may include source data checks. Therefore, direct access to the original source data will be required for inspections and/or audits. All inspections and audits will be carried out giving consideration to data protection as well as subject confidentiality to the extent that local, state, and federal laws apply.

## 9 SAFETY DEFINITIONS, SAFETY MONITORING AND REPORTING

### 9.1 Adverse Event

An adverse event (AE) is defined as any untoward medical occurrence associated with the use of a drug in humans, whether or not the event is considered drug-related. An AE can therefore be any unfavorable and unintended sign (e.g., an abnormal laboratory finding), symptom, or disease occurring after the subject started dosing with the study drug, without any judgment about causality. Any pre-existing medical condition that worsens after administration of the study drug will also be considered a new AE.

Study drug includes the investigational drug under evaluation and placebo.

AE collection will start following the first administration of study drug until the last follow up visit of the study.

Documentation regarding the AE should be made as to the nature, date of onset, end date, severity, relationship to study drug, action(s) taken, seriousness, and outcome of any sign or symptom observed by the Investigator or reported by the subject upon indirect questioning.

#### 9.1.1 Severity

Severity of an AE is defined as a qualitative assessment of the degree of intensity of an AE as determined by the investigator or reported to him/her by the patient/subject. The assessment of severity is made irrespective of relationship to study drug or seriousness of the event and should be evaluated according to the following scale:

- *Mild:* Event is noticeable to the subject but is easily tolerated and does not interfere with the subject's daily activities.
- *Moderate:* Event is bothersome, possibly requiring additional therapy, and may interfere with the subject's daily activities.
- *Severe:* Event is intolerable, necessitates additional therapy or alteration of therapy, and interferes with the subject's daily activities.

#### 9.1.2 Relationship to Study Drug

The relationship of each AE to the investigational product should be determined by the investigator (in a blinded manner) using these explanations:

- *Definite:* When there are good reason and sufficient documentation to demonstrate a direct causal relationship between investigational product and AE

OC-01 (varenicline) Nasal Spray  
Clinical Trial Protocol # OPP-101  
Amendment #1

Sponsor: Oyster Point Pharma, Inc.

- *Probable*: When there are good reasons and sufficient documentation to assume a causal relationship in the sense of plausible, conceivable, likely but not necessarily highly probable
- *Possible*: When there is sufficient information to accept the possibility of a causal relationship in the sense of not impossible and not unlikely, although the connection is uncertain or doubtful, for example; due to missing data or insufficient evidence.
- *None*: When there is sufficient information to accept a lack of a causal relationship, in the sense of impossible and improbable.
- *Unclassified*: When the causal relationship is not assessable for whatever reason due to insufficient evidence, conflicting data or poor documentation.

### 9.1.3 Expectedness

The expectedness of an AE should be determined based upon existing safety information about the study drug using these explanations:

- *Unexpected*: An AE that is not listed in the Investigator's Brochure (IB) or is not listed at the specificity or severity that has been observed.
- *Expected*: An AE that is listed in the IB at the specificity and severity that has been observed.
- *Not Applicable*: Any AE that is unrelated to the study drug.

AEs that are mentioned in the IB as occurring with a class of drugs or as anticipated from the pharmacological properties of the drug but are not specifically mentioned as occurring with the particular drug under investigation are to be considered unexpected.

The investigator should initially classify the expectedness of an AE, but the final classification is subject to the Medical Monitor's determination.

## 9.2 **Serious Adverse Events**

An AE is considered "serious" (SAE) if, in the view of either the investigator or Sponsor, it results in any of the following outcomes:

- Death
- A life-threatening AE

Note: An AE is considered "life-threatening" if, in the view of either the investigator or Sponsor, its occurrence places the patient or subject at immediate risk of death. It does not include an AE that, had it occurred in a more severe form, might have caused death.

- Inpatient hospitalization or prolongation of existing hospitalization

OC-01 (varenicline) Nasal Spray  
 Clinical Trial Protocol # OPP-101  
 Amendment #1

Sponsor: Oyster Point Pharma, Inc.

Note: The term “inpatient hospitalization” refers to any inpatient admission (even if less than 24 hours). For chronic or long-term inpatients, inpatient admission includes transfer within the hospital to an acute/intensive care inpatient unit. Inpatient hospitalization does not include: emergency room visits; outpatient/same-day/ambulatory procedures; observation/short stay units; rehabilitation facilities; hospice facilities; nursing homes; or clinical research/phase 1 units.

Note: The term “prolongation of existing hospitalization” refers to any extension of an inpatient hospitalization beyond the stay anticipated or required for the reason for the initial admission as determined by the investigator or treating physician.

- A persistent or significant incapacity or substantial disruption of the ability to conduct normal life functions

Note: An SAE specifically related to visual threat would be interpreted as any potential impairment or damage to the subject’s eyes (e.g., hemorrhage, retinal detachment, central corneal ulcer or damage to the optic nerve).

- A congenital anomaly/birth defect in an offspring of a study subject.

Important medical events that may not result in death, are life-threatening, or require hospitalization may be considered serious when, based upon appropriate medical judgment, they may jeopardize the patient or subject and may require medical or surgical intervention to prevent one of the outcomes listed in this definition.

SAEs are collected at the time the subject signs the Informed Consent Form until the last follow up visit of the study.

### 9.3 Procedures for Reporting Adverse Events

All AEs and their outcomes must be reported to [REDACTED] the Sponsor, and the IRB/IEC as required by the IRB/IEC, federal, state, or local regulations and governing health authorities and recorded on the appropriate eCRF.

#### 9.3.1 Reporting a Suspected Unexpected Adverse Reaction

All AEs that are ‘suspected’ and ‘unexpected’ are to be reported to [REDACTED] the Sponsor and the IRB/IEC as required by the IRB/IEC, federal, state, or local regulations and governing health authorities.

#### 9.3.2 Reporting a Serious Adverse Event

To ensure subject safety, all SAEs, regardless of relationship to the study drug, must be immediately reported. All information relevant to the SAE must be recorded on the appropriate CRFs. The investigator is obligated to pursue and obtain information requested by [REDACTED] and/or the Sponsor in addition to that information reported on the CRF. All subjects experiencing a SAE must be followed up and the outcome reported.

OC-01 (varenicline) Nasal Spray  
Clinical Trial Protocol # OPP-101  
Amendment #1

Sponsor: Oyster Point Pharma, Inc.

In the event of a SAE, the investigator must notify [REDACTED] and the Sponsor immediately; obtain and maintain in his/her files all pertinent medical records, information, and medical judgments from colleagues who assisted in the treatment and follow-up of the subject; provide [REDACTED] and the Sponsor with a complete case history, which includes a statement as to whether the event was or was not suspected to be related to the use of the study drug; and inform the IRB of the SAE within their guidelines for reporting SAEs.

Contact information for reporting SAEs:

Name:	[REDACTED]
Title:	Clinical Project Manager [REDACTED]
Company:	[REDACTED]
Office Telephone:	[REDACTED]
Mobile Telephone:	[REDACTED]
Office Facsimile:	[REDACTED]
Name:	[REDACTED]
Title:	Medical Monitor
Office Telephone:	[REDACTED]
Mobile Phone:	[REDACTED]
Office Facsimile:	[REDACTED]

**9.4 Procedures for Unmasking of Study Drug**

All subjects, investigators, and study personnel involved with the conduct of the study will be masked with regard to treatment assignments. When medically necessary, the investigator may need to determine what treatment regimen has been assigned to a subject. When possible (i.e., in non-emergent situations), [REDACTED] and/or the Sponsor should be notified before unmasking study drug. Unmasking will be performed utilizing the randomization system. The unmasked subject will continue the study if warranted by the Investigator in consultation with the Medical Monitor.

**9.5 Type and Duration of the Follow-up of Subjects after Adverse Events**

The investigator will follow unresolved AEs to resolution until the subject is lost to follow-up or until the AE is otherwise classified. Resolution means the subject has returned to baseline state of health or the Investigator does not expect any further improvement or worsening of the AE. If the patient is lost to follow-up, the Investigator should make 3 reasonable attempts to contact the patient via telephone, post, or certified mail. All follow-up

OC-01 (varenicline) Nasal Spray  
Clinical Trial Protocol # OPP-101  
Amendment #1

Sponsor: Oyster Point Pharma, Inc.

will be documented in the subject's source document. Non-serious AEs identified on the last scheduled contact must be recorded on the AE eCRF with the status noted.

If the Investigator becomes aware of any new information regarding an existing SAE (i.e., resolution, change in condition, or new treatment), a new SAE/Unanticipated Report Form must be completed and faxed to [REDACTED] within 24 hours of the site's awareness of the new information. The original SAE form is not to be altered. The report should describe whether the event has resolved or continues and how the event was treated.

## 10 STATISTICAL ANALYSIS

Statistical considerations and methods of analyses for this study are provided below; the accompanying Statistical Analysis Plan (SAP) contains complete details of the planned analyses.

### 10.1 Primary and Secondary Endpoints

#### Primary Endpoint:

- Percent of subjects who achieve  $\geq 10$  mm improvement in Schirmer's Test Score from baseline at Visit 4 (Day 28)

#### Secondary Endpoints

- Mean change from Baseline in Eye Dryness Score (EDS) at 5 minutes after threshold defined treatment administration in the Controlled Adverse Environment® Chamber at Visit 4 (Day 28)
- Mean change from Baseline in Eye Dryness Score (EDS) at Visit 4 (Day 28) (Post STS)
- Mean change from Baseline in Schirmer's Test Score (STS) at Visit 4 (Day 28)
- Mean change from Baseline in Corneal Fluorescein Staining at Visit 4 (Day 28)

### 10.2 Analysis Populations

#### 10.2.1 Intention-To-Treat Population

The intent-to-treat (ITT) population will include all randomized subjects. Analyses using the ITT population will group subjects according to the treatment to which they were randomized.

#### 10.2.2 Safety Population

The safety population will include all randomized subjects who received at least one dose of the study drug. Analysis on the safety population will group subjects according to the treatment actually received.

OC-01 (varenicline) Nasal Spray  
Clinical Trial Protocol # OPP-101  
Amendment #1

Sponsor: Oyster Point Pharma, Inc.

### 10.3 Statistical Hypotheses

Let  $p_l$ ,  $p_h$ , and  $p_p$  denote the percent of subjects in each group (low dose, high dose, and placebo, respectively) who have  $\geq 10$ mm change from baseline to Visit 4 in STS.

$$H_0: p_l - p_p = 0 \text{ or } p_h - p_p = 0$$

$$H_1: p_l - p_p \neq 0 \text{ or } p_h - p_p \neq 0$$

### 10.4 Sample Size and Power Considerations

The study will randomize approximately 750 subjects in a 1:1:1 ratio to the three treatment groups. Approximately 250 subjects in each treatment group are expected to complete their assigned treatment and have endpoint assessments at Visit 4.

For the primary endpoint, the percent of subjects achieving  $\geq 10$  mm improvement from Baseline in STS at Visit 4, the ONSET-1 study had roughly 15% of subjects in the placebo group and 50% in each of the 0.6 mg/ml and 1.2 mg/ml groups. If the true proportion achieving at least a 10 mm improvement is 15% in the placebo group and, conservatively, 40% in each of the active arms, the power for each dose would be greater than 99%.

The secondary endpoint is the EDS test. The ONSET-1 study showed a roughly 12 unit difference between placebo and each active treatment group in mean change from baseline to day 28 with a standard deviation (SD) of roughly 26 units. If these estimates apply to the Phase III ONSET-2 study and the data are analyzed with an analysis of variance, the study will have approximately 99% power for each dose.

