### Summary of Known and Potential Risks and Benefits to Human Subjects

The administration of OC-01 0.6 mg/mL and 1.2 mg/mL (varenicline) Nasal Spray was safe, well tolerated, and efficacious as assessed in the ONSET-1 study. The study met the primary endpoint (Schirmer's Test) for both the 0.6 mg/mL and 1.2 mg/mL dose groups. It also met the secondary symptom endpoints (EDS) for 0.6 mg/mL OC-01 (varenicline) Nasal Spray. There was not a statistically significant improvement in EDS in the normal environment at Day 28 for the 1.2 mg/mL dose, although there was a numerical benefit as compared to placebo. Because of the pre-specified hierarchical approach to multiplicity for the secondary outcomes, the EDS symptoms within the CAE® environment at Day 21 could not be formally tested; however, the data strongly suggest benefit on that outcome as well. Although the low dose of 0.12 mg/mL OC-01 (varenicline) Nasal Spray demonstrated statistical significance in Schirmer's Score in exploratory analyses, this dose did not yield statistically significant difference in the symptom endpoint in exploratory analyses as measured by EDS.

Showing statistical significance in both signs and symptoms of DED in the same study population is a goal seldom before achieved in the treatment of the disease. Importantly, after treatment with OC-01 (varenicline) Nasal Spray, improvements in EDS were seen as early as 5 minutes after administration in the CAE® in the 0.6 mg/mL and 1.2 mg/mL OC-01 (varenicline) Nasal Spray dose groups. Exploratory analyses of fluorescein corneal staining indicate a benefit in subjects treated with OC-01 (varenicline) Nasal Spray compared to those subjects treated with placebo.

OC-01 (varenicline) Nasal Spray was safe and well-tolerated at all concentrations assessed in the ONSET-1 clinical study. Most TEAEs were mild to moderate in severity, with only 1 subject reporting a severe TEAE.

The most common AE in all treatment groups was sneezing which was temporally related to the administration of the study drug and resolved within a short period of time after administration. Sneezing AEs were characterized as mild to moderate, with no severe AEs reported.

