**4 OVERALL STUDY DESIGN**

Protocol OPP-101 is a Phase 3, multicenter, randomized, controlled, double- masked study designed to evaluate the safety and efficacy of OC-01 (varenicline) Nasal Spray in adult participants with DED. Approximately 750 subjects at least 22 years of age with a physicians' diagnosis of dry eye disease and meeting all other study eligibility criteria will be randomized to receive an application of OC-01 (varenicline) Nasal Spray or placebo twice daily (BID) for 28 days with three additional long-term follow-up visits at 6 weeks, 6 months and 12 months.

Participants who terminate early during the application period will be asked to complete safety assessments (if the participants agree) prior to study exit. Participants who are terminated early from the study will not be replaced.

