### 8.6.3 Discontinued Subjects

Subjects may be discontinued from treatment, or from involvement in the study at any time prior to their completion of the study due to:

- Non-Fatal Adverse Event;
- Protocol Violations;
- Lost to Follow-up;
- Physician Decision;
- Subject Non-compliance;
- Death;
- Study Terminated by sponsor;
- Withdraw by Subject (e.g. withdrawal of consent); and
- Other

Note: In addition, any subject may be discontinued from treatment or from study involvement from any sound medical reason at the discretion of the investigator (after consultation with the Sponsor) or Sponsor.

Notification of a subject discontinuation and the reason for discontinuation will be made to [REDACTED] and/or Sponsor and will be clearly documented on the eCRF.

If the subject discontinues from treatment, they will be asked to be followed for safety for the duration of the study, unless they refuse to attend follow-up visits. Subjects will be asked to attend Visit 4b, Visit 5, Visit 6 and Visit 7 and have all scheduled assessments performed as per the Schedule of Visits and Measurements ([Appendix 1](#))

Discontinued subjects will not be replaced.

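### Does expecting about 250 completers per arm from about 250 randomised, with a 12-unit EDS effect for both doses, overstate the trial's power?

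*Protocol*

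**What the plan says.** On numbers, Protocol 10.4 says "The study will randomize approximately 750 subjects in a 1:1:1 ratio to the three treatment groups", and continues: "Approximately 250 subjects in each treatment group are expected to complete their assigned treatment and have endpoint assessments at Visit 4". SAP section 7 repeats the expectation. Protocol 8.6.3 adds "Discontinued subjects will not be replaced", and Protocol section 4 says the same of early terminations: "Participants who are terminated early from the study will not be replaced". For subjects who stop treatment, Protocol 8.6.3 provides: "Subjects will be asked to attend Visit 4b, Visit 5, Visit 6 and Visit 7 and have all scheduled assessments performed".

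On effects, Protocol 10.4 takes the primary responder rate as 15% on placebo. It lowers the active rate from the roughly 50% seen in ONSET-1 to 40%, and claims more than 99% power for each dose. For EDS it writes: "The ONSET-1 study showed a roughly 12 unit difference between placebo and each active treatment group in mean change from baseline to day 28". With an SD of roughly 26 units it claims about 99% power for each dose, provided the ONSET-1 estimates carry over.

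The Summary of Known and Potential Risks and Benefits in the protocol reports that 0.6 mg/mL met its EDS endpoints in ONSET-1. Of the higher dose it says: "There was not a statistically significant improvement in EDS in the normal environment at Day 28 for the 1.2 mg/mL dose". It adds that 1.2 mg/mL was numerically better than placebo.

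**The concern.** Two things look wrong. First, the same figure of about 250 per arm serves for subjects randomised and for subjects completing. Without replacement that is 0% attrition. Yet SAP 9.8 lists ten reasons for discontinuation, and SAP Appendix 2 is devoted to multiple imputation for the secondary endpoints. If power had been worked out on completers who will not exist, it would be too high.

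Second, the EDS effect is carried over at full size to both doses. One of them did not reach significance at Day 28, the time point to which the 12 units refer. The same section trims the Schirmer response rate for caution but leaves the less certain symptom effect untrimmed. If the true 1.2 mg/mL effect were well below 12 units, a power of about 99% would give false comfort, and a null symptom result for that dose could be over-read as evidence of no effect.

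**Working it through.** **Inputs.** From Protocol 10.4: 250 per arm; EDS difference 12, SD 26; responder rates 15% and 40%. The hypotheses are two-sided. The significance level is not legible in the public text, so 0.05 two-sided is assumed, with 0.025 as a variant.

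**1. Implied attrition.** 750 / 3 = 250 randomised per arm. With 250 expected to complete, 1 − 250/250 = 0%.

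**2. The plan's own EDS figure.** Power = Φ(δ / [SD × √(2/n)] − 1.96).
- SE = 26 × √(2/250) = 2.3255
- 12 / 2.3255 = 5.160
- 5.160 − 1.96 = 3.200, so power = 99.93%

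The noncentral t gives the same 99.93%. At alpha 0.025 it is 99.82%. The plan's figure of about 99% reproduces and is slightly cautious.

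**3. The plan's own primary figure.** The pooled rate is 0.275.
- Null SE = √(2 × 0.275 × 0.725 / 250) = 0.03994
- Alternative SE = √((0.15 × 0.85 + 0.40 × 0.60) / 250) = 0.03834
- (0.25 − 1.96 × 0.03994) / 0.03834 = 4.479, so power exceeds 99.99%

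**4. Attrition, with lost subjects dropped.** Effects as planned:

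| Loss | n per arm | EDS power | Primary power |
|---|---|---|---|
| 0% | 250 | 99.93% | >99.99% |
| 10% | 225 | 99.83% | >99.99% |
| 15% | 212 | 99.74% | >99.99% |
| 20% | 200 | 99.60% | 99.99% |

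The n that gives exactly 99% EDS power is 2 × (1.960 + 2.326)² × 26² / 12² = 172.5, so 173 per arm. That is a loss of 1 − 173/250 = 31%. At alpha 0.025 it is 196 per arm, a loss of 22%.

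**5. Attrition, read more harshly.** Keep all 250 per arm in the analysis, but let 20% contribute no benefit.
- EDS: 12 × 0.8 = 9.6 units; 9.6 / 2.3255 − 1.96 = 2.168; power 98.5%.
- Primary, with the lost 20% counted as non-responders: 15% and 40% become 12% and 32%. The null SE is 0.03705 and the alternative SE 0.03596, so (0.20 − 1.96 × 0.03705) / 0.03596 = 3.54 and power is 99.98%.

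**6. Does missing significance contradict 12 units?** In an unadjusted comparison, 12 units with SD 26 is non-significant at 0.05 when n < 2 × (1.96 × 26 / 12)² = 36.07. The t-test puts the boundary at 37 per arm (p = 0.051, 95% CI −0.05 to 24.05). The documents give no ONSET-1 arm sizes, dose-specific EDS estimates or analysis model. So an imprecise estimate near 12 and a smaller estimate are both possible.

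**7. If the 1.2 mg/mL effect were smaller.** These effects are assumptions; none comes from the documents. The 8.6 row borrows the Schirmer discount: a difference of 35 points cut to 25 gives 12 × 25/35 = 8.6.

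| True EDS effect | 250 per arm | 225 per arm |
|---|---|---|
| 10 | 99.0% | 98.3% |
| 8.6 | 95.8% | 93.8% |
| 8 | 93.1% | 90.4% |
| 6 | 73.2% | 68.7% |

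At 250 per arm, 90% power needs about 7.5 units and 80% about 6.5.

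**The case for a change.** The best case for a change runs as follows. Rounding does not reconcile 250 randomised with 250 completing, because the same rounded number is used for both. Follow-up after stopping treatment cannot turn a subject into a treatment completer. Discontinued subjects are asked back to Visit 4b but not Visit 4a, where the first-listed secondary endpoint, EDS in the controlled adverse environment (CAE), is measured. No power is given for that endpoint in the readable text. And a stated 99% implies about a 1% chance of missing the effect, whereas at 6 units the chance is 27% to 31%.

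Part of this stands. The completer count is optimistic, the 12 units are undiscounted, and the 1.2 mg/mL effect is uncertain. But step 4 shows that the count has almost no bearing on the claimed power, and the request to attend Visit 4b preserves some of the Schirmer and EDS data there. The EDS claim is openly conditional, so leaving the effect untrimmed is an asymmetry of presentation and not an error. Carrying a percentage discount from a responder rate to a symptom score is a choice without support in the documents, and it still leaves 94% to 96% power. Only the 6-unit case drops power sharply, and nothing in the documents points to 6.

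Which EDS is meant can be worked out. The 12 units are a Day 28 figure, and the protocol's account of ONSET-1 puts the normal-environment EDS at Day 28 and the CAE EDS at Day 21. A null 1.2 mg/mL result would in any case be read from its estimate and confidence interval, not from a planning figure.

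**Conclusion.** No change follows. The absence of an attrition allowance is a loose statement in the sample size text. It does not disturb the stated powers: at 20% loss EDS power is 99.6% with lost subjects dropped, or 98.5% if they remain and contribute no benefit, and primary power is above 99.9% either way. The EDS figure is arithmetically right and conditional on its inputs. What remains is ordinary planning uncertainty about the 1.2 mg/mL symptom effect. It would bring power below 99% only if the true effect were under about 10 units at 250 per arm. The documents cannot say whether it is.

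Writing in about 225 evaluable per arm at 10% loss, or printing a range of EDS powers, would be a courtesy to readers. It would alter neither enrolment nor analysis nor the interpretation of results.

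This rests on a two-sided 0.05 level (conclusions are similar at 0.025, where EDS power is 99.1% at 200 per arm), an SD of 26, simple unadjusted comparisons, and equal loss across arms. The SAP's text on missing data and multiplicity is redacted, as is its analysis text for the primary and secondary endpoints, so how lost subjects enter the analyses could not be checked beyond the two readings shown.
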